Attachment 15a. Multi-site Study Child Questionnaire — Short Form

(best completed by the child's birth mother who is also an adult participant)

Form Approved OMB No. 0923-XXXX Exp. Date xx/xx/201x

ATSDR estimates the average public reporting burden for this collection of information as 15 minutes per response, including the time for reviewing instructions, searching existing data/information sources, gathering and maintaining the data/information needed, and completing and reviewing the collection of information. An agency may not conduct or sponsor, and a person is not required to respond to a collection of information unless it displays a currently valid OMB Control Number. Send comments regarding this burden estimate or any other aspect of this collection of information, including suggestions for reducing this burden to CDC/ATSDR Information Collection Review Office, [name]; ATTN: PRA (0923-xxxx).

Adult Study ID No.	(alias)
Parent Study ID No.	
Child Study ID No.	

Section A: Demographic Information

A1. What is your relationship to your child?

____Birth mother

____Birth father

____Adoptive mother

____Adoptive father

____Legal guardian

____Other relationship: specify _____

____Refused to answer

A2. What is your child's sex?

____Male

____Female

____Refused to answer

A3. What is your child's date of birth?

__(MM/DD/YYYY)

____Refused to answer

A4. Do you consider your child to be Hispanic or Latino?

____Yes

____No

____Refused to answer

A5. What race do you consider your child to be? Mark all that apply.

____American Indian or Alaska Native

____Asian

- ____Black or African American
- ____Native Hawaiian or Other Pacific Islander
- ____White
- ____Refused to answer
- A6. What is the highest grade level of education your child has completed? ____grade
- A.7 What is the highest level of education you completed?
- Less than high school
- ____Some high school
- ____High school graduate or equivalent (GED)
- ____Some university/college
- ____Technical or trade school
- ____University/college graduate
- ____Graduate school or higher
- A8. What is the child's household income (from all sources)?
- ____Less than \$25,000
- ____\$25,000 to \$69,000
- ____\$70,000 to \$149,000
- ____More than \$150,000
- ____Don't know
- ____Refused to answer

A9. During the last 12 months did the child have any kind of health insurance?

- ___Yes
- ___No
- ____Don't know
- ____Refused

Section B: Residential History and Drinking Water Exposures

B1. On average, how many 8 oz. cups of tap water or beverages prepared with tap water does your child currently drink per day at home?

____ cups

____Didn't drink tap water

____Don't know

____Refused to answer

Note: 1 cup = 8 oz.; 2 cups = 1 pint (16 oz.); 4 cups = 1 quart (32 oz.); 16 cups = 1 Gallon (128 oz.)

B2. Please fill out the table below for all residences that your child has lived.

Street Address, City, State	Your child's	Move in	Main source of
	average	(mm/yy)	tap water at
	consumption of		this address
	tap water per		(public water
	day (# cups) at		system or
	this address		private well?)

B3. When [you were/the child's birth mother was] pregnant with your child, on average how many 8

oz. cups of tap water or beverages prepared with tap water did [you/she] drink per day?

____ cups

___Didn't drink tap water

____Don't know

____Refused to answer

B4. When [you were/the child's birth mother was] breastfeeding your child, on average how many 8

- oz. cups of tap water or beverages prepared with tap water did [you/she] drink per day?
- ____ cups
- ____Didn't drink tap water
- ____Don't know
- ____Refused to answer
- ____Did not breastfeed my child

Section C: History of Potential Exposure Modifiers

This next set of questions is for the child's birth mother about the child. If you are not her, we can follow up after this interview with a quick phone call to complete the questionnaire.

- C1. Has your child ever had a blood transfusion?
- ____Yes ightarrow Please specify how many times your child had a blood transfusion______
- ___No →go to Question C3
- ___Don't know →go to Question C3
- ____Refused to answer →go to Question C3
- C2. When did your child last have a blood transfusion?

_____month/year

- C3. Has your child ever donated blood?
- ____Yes → Please specify how many times your child has donated blood______
- ___No \rightarrow go to Section D.
- ____Don't know \rightarrow go to Section D.
 - ___Refused to answer \rightarrow go to Section D.
- C4. When did your child last donate blood? _____ Month/Year

C5. On average, how often does your child donate blood in a year?

Section D: Occupational History of the Child

This next set of questions is for the child's birth mother about the child. If you are not her, we can follow up after this interview with a quick phone call to complete the questionnaire.

D1. Has your child been employed for at least one month at a job?

____Yes

___No \rightarrow go to Section E.

Job information	Job 1	Job 2	Job 3
a. Where did your child work?			
(City, State)			
b. Name of employer			
c. Start date (month, year)			
d. End date (month, year)			
e. Job title/description			
f. Did your child work with or around radiation or any chemicals at this job such as solvents, metals,	Yes (Please specify)	Yes (Please specify)	Yes (Please specify) No
asbestos, or pesticides?	Don't know	on't know	Don't know

D2. On average how many 8 oz. cups of tap water or beverages prepared with tap water did [he/she] drink per day at work?

____ cups

____Didn't drink tap water

____Don't know

____Refused to answer

Note: 1 cup = 8 oz.; 2 cups = 1 pint (16 oz.); 4 cups = 1 quart (32 oz.); 16 cups = 1 Gallon (128 oz.)

Section E: Child's Daycare/School History

E1. Did your child attend day care?

____Yes

No \rightarrow go to Question E3

____Don't know \rightarrow go to Question E3

_____Refused to answer \rightarrow go to Question E3

E2. Please fill out the table below for the day care centers your child attended.

Day care (name)	Street Address, City, State	Start Date (mm/yy)	End Date (mm/yy)	Child's average consumption of tap water per day (# cups)

Note: 1 cup = 8 oz.; 2 cups = 1 pint (16 oz.); 4 cups = 1 quart (32 oz.); 16 cups = 1 Gallon (128 oz.)

E3. Please fill out the table below for the schools your child has attended. If your child was home schooled, please go to Section F

School (name)	Street Address, City, State	Start	End	Child's average
		Date	Date	consumption of tap
		(mm/yy)	(mm/yy)	water per day (# cups)

Note: 1 cup = 8 oz.; 2 cups = 1 pint (16 oz.); 4 cups = 1 quart (32 oz.); 16 cups = 1 Gallon (128 oz.)

Section F: Child's Medical History

F1. Have you ever been told by a doctor or other health care provider that your child has or had any of the following medical conditions? Fill out the table below. Circle appropriate response and ask the respondent to specify as directed.

	Medical condition		If yes, what year was your child diagnosed?
a.	Cancer?	Yes (Please specify) No Don't know	year
b.	Allergies?	Yes (Please specify) No Don't know	year
C.	Atopic dermatitis/eczema?	Yes (Please specify) No Don't know	year
d.	Asthma?	Yes No Don't know	year
e.	Chronic stuffy/runny nose (rhinitis/sinusitis)?	Yes No Don't know	year
f.	High cholesterol?	Yes No Don't know	year
g.	Thyroid disease?	Yes (Please specify) No Don't know	year
h.	Delayed puberty?	Yes (Please specify) No Don't know	year
i.	Obesity?	Yes No Don't know	year
j.	Lupus	Yes No Don't know	year
k.	Celiac disease	Yes No Don't know	year
I.	Crohn's disease	Yes No Don't know	year
m.	Diabetes	Yes, Type 1 Yes, Type 2 Yes, Type unknown No Don't know	year

	Medical condition		If yes, what year was your child diagnosed?
n.	Scleroderma	Yes No Don't know	year
0.	Attention deficit hyperactivity disorder (ADHD) or attention deficit disorder (ADD)?	Yes No → go to p Don't know → go to p	year
р.	How is your child treated for ADHD or ADD?		year
q.	Other learning or behavioral problems?	Yes (Please specify) No → go to Question B2. Don't know → go to Question B2.	year
r.	How is your child treated for their learning or behavioral problems?		

F2.. What age was your child last vaccinated for:

Diphtheria, Tetanus, Pertussis ("DTaP")	age	Don't know	never was vaccinated
"Tdap" booster Tetanus, Diptheria, Pertussis	sage	Don't know	never was vaccinated
Measles, Mumps, Rubella ("MMR")	age	Don't know	never was vaccinated
Tetanus shot (for a puncture wound or cut)	age	Don't know	never was vaccinated

FOR GIRLS ONLY

F3. Has your daughter ever used an oral contraceptive ("birth control pill")?

- ____Yes
- ___No → go to Question E5
- ____Don't know \rightarrow go to Question E5
- ____Refused to answer \rightarrow go to Question E5

F4. When did your daughter last use an oral contraceptive ("birth control pill")?

__Month/Year

F5. At what age did your daughter begin menstruation (have her first period)?

____Age

____Has not yet begun to menstruate \rightarrow go to Section G

___Don't know

F6. Does your daughter's period occur regularly (every month)?

___Yes

- ____No, it is irregular
- ____No, she does not have a period \rightarrow go to Question E10
- ____Don't know \rightarrow go to Question E10
- F7. How many days has been your daughter's cycle on average during the last year?
- ____>26 days
- ____27-29 days
- ____30-32
- ____>32 days
- ____Don't know
- F8. Can you characterize your daughter's usual period flow during the last year?
- ___Light
- ____Medium
- ____Heavy
- ____Don't know
- F9. When was your daughter's last period before this study blood draw? Date:
 - __Don't know
- F10. Has your daughter ever been pregnant?
- ___Yes
- ___No → go to Section G
- ____Don't Know \rightarrow go to Section G
- ____Refused to answer \rightarrow go to Section G

F11. How many times has your daughter been pregnant?

	Pregnancy #1	Pregnancy #2	Pregnancy #3
a. What month and year did this pregnancy start?	/	/	/
b. What month and year did this pregnancy end?	/	/	/
c. Did the pregnancy result in a live birth?	Yes	Yes	Yes
	No (go to g)	No (go to g)	No (go to g)
	Don't Know	Don't Know	Don't Know

d. Did your daughter breastfeed the child?	Yes	Yes	Yes
	No (go to g)	No (go to g)	No (go to g)
	Don't Know	Don't Know	Don't Know
e. How long did your daughter breastfeed the child?	months	months	months
f. When did your daughter stop breastfeeding the			
child?	monthyear	monthyear	monthyear
g. Did a doctor or nurse say that your daughter had	Yes	Yes	Yes
pre-eclampsia during her pregnancy?	No	No	No
	Don't know	Don't know	Don't know
h. Did a doctor or nurse say that your daughter had	Yes	Yes	Yes
pregnancy-induced hypertension?	No	No	No
	Don't know	Don't know	Don't know
i. Did a doctor or nurse say that your daughter had	Yes	Yes	Yes
gestational diabetes?	No	No	No
	Don't know	Don't know	Don't know

Section G: Family Medical History

G1. Have any of your child's blood relatives - grandparents, parents, or siblings - ever been told by a health professional that they have or had any of the following conditions? Fill out the table below. Circle appropriate response and ask the respondent to specify as directed.

	Modical condition		If yes, ask: Which relative
			had this condition?
		Yes	Grandparent
a. Obesity	No	Parent	
		Don't know	Sibling
 b. Attention deficit hyperactivity disorder (ADHD or attention deficit disorder (ADD) 	Attention deficit hyperactivity	Yes	Grandparent
	No	Parent	
	Don't know	Sibling	
c. C p	Other learning or behavioral problems	Yes	Grandparent
		No	Parent
		Don't know	Sibling

CONCLUSION: That completes this survey. I would like to sincerely thank you for your time.

Multi- Blood Drav	Form Approved OMB No. 0923-XXXX Exp. Date xx/xx/201x	
ATSDR estimates the average public reporting burden for this of instructions, searching existing data/information sources, gath the collection of information. An agency may not conduct or sp displays a currently valid OMB Control Number. Send commen including suggestions for reducing this burden to CDC/ATSDR I 30333; ATTN: PRA (0923-xxxx).	collection of information as 10 minutes per re ering and maintaining the data/information oonsor, and a person is not required to respo ts regarding this burden estimate or any oth nformation Collection Review Office, 1600 Cl	esponse, including the time for reviewing needed, and completing and reviewing and to a collection of information unless it er aspect of this collection of information, lifton Road NE, MS D-74, Atlanta, Georgia
Adult Study ID No.:	OR Child Study ID No.: _	
You were asked to collect a first morning v	oid urine sample when you got	up today.
1. Did you bring it today?		🗆 Yes 🗆 No
1a. [IF NO] Can you give us a sample	e now?	🗌 Yes 🗌 No
2. Result of the urine collection (mark one)	Volume	
Complete	(at least 10-mL)	
Partial	2a. (mL)	
Unable to collect		
Before we can take [your/your child's] blo [you/your child] can provide a blood samp	od we need to ask you a few qu le.	estions on whether
3. [Do you/Does your child] have hemophilia?		🗆 Yes 🗖 No
4. [Have you/Has your child] received any c	hemotherapy in the last four we	eks? 🗌 Yes 🗌 No
5. [Do you/Does your child] have active som arm/shoulder that could prevent us from	es, disease, or other problem on n taking a blood sample*?	the 🗌 Yes 🗌 No
* This may include gauze dressings casts ed	ema naralysis tubes onen sores o	wounds withered arms or

* This may include gauze dressings, casts, edema, paralysis, tubes, open sores or wounds, withered arms or limbs missing, damaged, sclerosed or occluded veins, allergies to cleansing reagents, burned or scarred tissue, shunt or intravenous lines on both arms. Please check and review all with the participant.
[IF THE ADULT/PARENT OR GUARDIAN RESPONDED 'YES' TO ANY OF THE ABOVE QUESTIONS, THE PARTICIPANT SHOULD BE EXCLUDED FROM THE BLOOD DRAW. PLEASE SEE STUDY COORDINATOR IMMEDIATELY.

SENIOR SUPERVISING NURSE WILL MAKE THE DECISION WHETHER A PARTICIPANT WITH ANY TYPE OF SHOULDER LESIONS CAN SAFELY PROVIDE A BLOOD SAMPLE]

We also want to ask you a few more questions as a precaution.

5. [Are you/Is your child] on blood thinning medication?		🗆 Yes 🗆 No
7. Are you on diabetes medication or insulin?		🗆 Yes 🗌 No
8. Tell me the last time you ate. Was it less than	n eight hours ago?	🗆 Yes 🗌 No
8a. [IF YES] How long ago did you eat?	: (hours and minutes)	
8b and what did you eat?	I	
[IF THE PARTICIPANT ANSWERED 'YES' TO ANY COORDINATOR AND SUPERVISING NURSE TO M	OF THE ABOVE QUESTIONS PLEASE SEE S IAKE SURE THEY CAN SAFELY PROVIDE BI	TUDY LOOD SAMPLE]
9. Result of the Blood Draw (mark one)	Volume	
□ Complete	(35-mL adults/25 ml children)	
Partial	7a. (mL)	
Unable to collect		
9a. Date: _ / / 9b. Tin	ne: _ : 🗆 AM 🗆 PM	
9c. Code Partial/Inability to Collect (circle one)		
Reason for partial or inability to collect blood:		
 Pregnant Medical (e.g. patient frail, weak, lost consciousness) Refused 		
4. Other (describe)		

NOTES: Care should be used in drawing blood from all subjects. Common adverse effects include bruising, bleeding, and fainting. Please ask all participants whether they prefer to lie down to have blood drawn.

Ask everyone if they tend to faint when giving blood. Suggest they sit down for five minutes after giving blood.

Fasting diabetic participants who use insulin will be given priority appointments for their blood draw.

Light snacks will be provided following blood collection.

See Protocol Attachment 14 (Manual of Operations) for further details on collecting blood samples.

[ON INVESTIGATORS INSTITUTION LETTERHEAD] [DATE]

[NAME OF PROVIDER] [ADDRESS] [CITY, STATE ZIP CODE]

Subject: Medical verification and records review for Multi-site PFAS Health Study

Dear [NAME OF PROVIDER]:

The Agency for Toxic Substances and Disease Registry (ATSDR) and [insert institution name] are conducting a research study of the health effects from exposure to per- and polyfluoroalkyl substances (PFAS) found in drinking water. We are working with the assistance of your local health department [insert name] and [name of all other partners]. ATSDR and research partners are conducting this research study with oversight from the CDC/ATSDR Institutional Review Board (IRB) under CDC Protocol No. xxxxxxx.

Under Section 8006 of the 2018 Consolidated Appropriations Act, Congress authorized ATSDR to study the impact that exposure to PFAS in drinking water might have on the health of affected citizens. This study will see if there is an increase of symptoms or illness related to these chemicals.

We plan to recruit a total of 6,000 adults and 2,000 children for the Multi-site PFAS Health Study. Those person had to reside in areas served by PFAS contaminated drinking water or were exposed in utero or during breastfeeding when the mother consumed the contaminated drinking water. Drinking water exposure must have occurred within 15 years of the start of the study. Persons who were ever employed as a firefighter, ever participated in fire training exercises using AFFF foam, or were ever employed at industrial facilities that used PFAS chemicals in the manufacturing process will be excluded.

[ADULT PARTICIPANT'S NAME or PARENT OR GUARDIAN'S NAME] has given the study investigators authorization to conduct a medical records review. ATSDR is interested in more information about [ADULT PARTICIPANT'S NAME/CHILD PARTICIPANT'S NAME]'s self-reported health conditions that may be related to chemical exposure. We have included an abstraction form for your office to fill out and return to us in the enclosed return envelope.

If we need additional information, the ATSDR/[institution name] study team may wish to review the medical records in your office. We would appreciate your assistance if this is necessary.

ATSDR is an agency of the U.S. Department of Health and Human Services. ATSDR is performing this activity as a public health authority as defined by the Health Insurance Portability and Accountability Act (HIPAA) [45 CFR §164.501]. The requested information represents the minimum necessary to carry out the public health purposes of this study as described in 45 CFR §164.514(d) of the Privacy Rule. The research is also covered by a Certificate of Confidentiality under Section 301(d) of the Public Health Service (PHS) Act, as amended by Section 2012 of the 21st Century Cures Act, P.L. 114-255 (42 U.S.C. 241(d))

For questions about this research study, please call the ATSDR study lead, [name], at [study telephone number]. Please leave a message with your name and a telephone number or address.

Thank you for your assistance.

[name], PhD

[name], DSc

Co-Principal Investigators Pease Study

Multi-site Study

Medical Record Abstraction Form Adult

Form Approved OMB No. 0923-XXXX Exp. Date xx/xx/201x

ATSDR estimates the average public reporting burden for this collection of information as 20 minutes per response, including the time for reviewing instructions, searching existing data/information sources, gathering and maintaining the data/information needed, and completing and reviewing the collection of information. An agency may not conduct or sponsor, and a person is not required to respond to a collection of information unless it displays a currently valid OMB Control Number. Send comments regarding this burden estimate or any other aspect of this collection of information, including suggestions for reducing this burden to CDC/ATSDR Information Collection Review Office, [name]; ATTN: PRA (0923-xxxx)).

Medical Record Abstraction Form - Adult

Study ID: []	Participant Name: []	Date of Birth:///	SSN: xxx-xx-xxxx
--------------	----------------------	-------------------	------------------

The person named above, or his or her legal representative, has authorized you to release his or her medical records to ATSDR/[institution name] for research purposes. Please check If you have a record that a doctor or other health care provider diagnosed or is treating any of the following medical conditions.

Please fill out the table below. Circle appropriate response and specify requested details as directed. Thank you.

Medical Condition	Record Located (Comments)	Year of Diagnosis or Treatment
a. High cholesterol?	Yes No	
b. Other dyslipidemia?	Yes (Please specify diagnosis) No	
c. Heart disease?	Yes No	
d. Hypertension?	Yes No	
e. Pregnancy induced hypertension?	Yes No	
f. Thyroid disease?	Yes (Please specify diagnosis) No	

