water purveyor on the distribution system characteristics, in particular, whether the PFAS concentrations can be assumed to be relatively uniform throughout the system or whether the system had specific areas with substantially higher or lower PFAS concentrations. If uniform PFAS concentrations can be assumed, then a random sample of households may be conducted and recruitment letters mailed to these households. If the system has specific areas with substantially higher PFAS concentrations, then households in these areas will be targeted (oversampled) for recruitment letters.

For sites with contaminated private wells, the recipient will request information on the impacted residences and the results of PFAS sampling of their private wells from the state and/or local health and environmental agencies. Sampling will target households based on the magnitude of the PFAS concentrations in their private wells – i.e., wells with higher concentrations will be oversampled.

11 Recruitment letters will provide a phone number to call for information about the study and to accept the 12 invitation to participate in the study. The recipient will screen each interested caller using an eligibility 13 screening script (**Attachment 4**). If necessary to achieve a high participation rate and the sampling size 14 goal for the site, study staff may visit the sampled households to recruit participants.

Sampled households may have more than one eligible adult and/or child, and some parents may want to
 enroll in both of the adult and child studies. Trained study staff will use the recruitment tracking form
 (Attachment 6) to track recruitment success and to calculate non-response bias.

18

19 3.5.3 Enrollment Procedures

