The residual blood specimens will be stored with the study-generated ID only. ATSDR will keep a separate dataset that can link the study ID with the participant's name. If participants change their minds later about letting their blood used for additional analyses, they can contact ATSDR and we will remove their specimens. We do not plan to provide participants the results of these future tests, but we may contact them if we learn something that is important.

27 3.8.7 Future Exploratory Analyses

- 1 CDC IRB approval will be sought for this additional research either as a protocol amendment or under a
- 2 new research protocol prior to undertaking this plan.

3 **3.9 Exposure Estimation**

4 The study will use the fasting serum PFAS measurements obtained from study participants to estimate 5 exposures. In addition, the study will estimate each participant's cumulative PFAS serum level, using:

- PFAS serum measurements obtained in the study,
- Historical reconstruction of PFAS concentrations in the drinking water consumed by the
 participant,
- 9 Questionnaire data on the participant's consumption of PFAS-contaminated drinking water and
 10 factors that might affect PFAS serum levels,

• Age-, sex-, and calendar year-specific "background" PFAS serum levels from NHANES, and

12 • Physiologically based pharmacokinetic (PBPK) models.

13 If previous PFAS serum measurements are available for some of the participants (e.g., from a 14 biomonitoring program), then these results will be used to validate the modeled historical PFAS serum 15 estimates.

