 the source via ground water, then the recipient should seek information on the extent of the
 contamination plume from the state environmental agency, EPA, and/or the industrial facility.

If the contaminated drinking water is from a municipal system, then the characteristics of the distribution system will be obtained from the water purveyor. If supply wells are used, then the recipient will request historical and current information on these wells including monthly or daily production logs and dates of operation. If a surface water source is used or if water is purchased from another purveyor, then the recipient will request information about this source.

10 The recipient will also request the results of all relevant PFAS sampling: in the surface water near the 11 drinking water intakes, in the distribution system, in the supply wells and nearby monitoring wells, in 12 purchased water from other water purveyors, and in the private wells in the study area.

13

14 **3.10 Statistical Analyses**

15 ATSDR staff will perform statistical analyses with the participation of the recipients using SAS, R and STATA 16 on the combined multi-site study dataset. ATSDR staff may also use SPSS for data management. ATSDR 17 staff will calculate descriptive statistics (including means, geometric means, medians, standard deviations, 18 and percentiles) to identify the presence and distribution of PFAS and effect biomarker analytes. Statistical 19 methods will include multiple linear regression of continuous (untransformed and natural log transformed) effect biomarkers on continuous (untransformed and natural log transformed) PFAS serum 20 21 levels and categorized PFAS serum levels, and logistic regression of categorized effect biomarkers (e.g., 22 hypercholesterolemia) or disease prevalence on continuous (untransformed and natural log transformed) 23 and categorical PFAS serum levels. ATSDR staff will use restricted cubic spline methods (or generalized 24 additive models using cubic regression splines) for linear and logistic regression to obtain flexible, 25 smoothed exposure-response curves. To identify risk factors that may act as confounders for a particular health outcome, the analysis will implement a "10% change in the estimate" rule (Maldonado 1993). 26

Primary analyses will focus on estimated cumulative PFAS serum levels. Supplemental analyses will
evaluate PFAS serum levels in the blood specimens obtained in the study as well as estimated maximum

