Section B: Residential History and Drinking Water Exposures

This next set of questions is about the child and the child's birth mother. If you are not her, we can follow up after this interview with a quick phone call to complete the questionnaire.

B1. What is the main source of tap water in your home?

____Public water system

____Private well

____Other: specify _____

____Don't know

_____Refused to answer

B2. On average, how many 8 oz. cups of tap water or beverages prepared with tap water does your child currently drink per day at home?

____ cups

____Doesn't drink tap water

____Don't know

____Refused to answer

Note: 1 cup = 8 oz.; 2 cups = 1 pint (16 oz.); 4 cups = 1 quart (32 oz.); 16 cups = 1 Gallon (128 oz.

B3. On average, how many 8 oz. cups of tap water or beverages prepared with tap water do you currently drink per day at home?

____ cups

____Doesn't drink tap water

____Don't know

Refused to answer

Note: 1 cup = 8 oz.; 2 cups = 1 pint (16 oz.); 4 cups = 1 quart (32 oz.); 16 cups = 1 Gallon (128 oz.

B4. What was your previous address?

Street	Apt	
City	State	Zip Code:

B5. When did you move into your previous address? Month____ Year_____

B6. What was the main source of tap water at that address?

____Public water system

____Private well

____Other: specify _____

____Don't know

_____Refused to answer

B7. On average, how many 8 oz. cups of tap water or beverages prepared with tap water did your child drink per day when living at your previous address?

____ cups

_Don't drink tap water

Don't know

____Refused to answer

____Your child did not live at this address

Note: 1 cup = 8 oz.; 2 cups = 1 pint (16 oz.); 4 cups = 1 quart (32 oz.); 16 cups = 1 Gallon (128 oz.

B8. Have you or your child lived at any other address since January 2000?

___Yes

__No → go to Section C

____Don't know \rightarrow go to Section C

____Refused to answer \rightarrow go to Section C

B9. Please fill out the table below for these other residences where you or your child lived since January 2000.

Street Address, City, State	Did your	Your child's average	Move in	Main source of
	child live	consumption of tap	(mm/yy)	tap water at
	at this	water per day (# cups)		this address
	address?	at this address		(public water
				system or
				private well?)

Note: 1 cup = 8 oz.; 2 cups = 1 pint (16 oz.); 4 cups = 1 quart (32 oz.); 16 cups = 1 Gallon (128 oz.

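### Neither child form records home filtration of tap water, so the water-borne part of the primary exposure may be overstated by an unknown amount; the gap is firm for long-form children

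*Protocol*

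**What the plan says.** **Long form (Attachment 15, Section B).** For the current home it asks "What is the main source of tap water in your home", then cups of tap water per day. For the previous home it asks address, move-in date, source and cups. B9 then says "Please fill out the table below for these other residences where you or your child lived since January 2000" and tabulates address, whether the child lived there, cups per day, move-in date and source. B10 and B11 ask the mother's tap cups per day in pregnancy and while breastfeeding.

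**Short form (Attachment 15a, Section B).** B1 asks the child's current cups at home. B2 says "Please fill out the table below for all residences that your child has lived", with columns for cups per day, move-in date and source. B3 and B4 repeat the two maternal items.

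**Use of the answers.** Section 3.9 estimates each participant's cumulative serum level from several inputs: "PFAS serum measurements obtained in the study"; "Historical reconstruction of PFAS concentrations in the drinking water consumed by the" participant; questionnaire data on consumption and on factors that affect serum levels; NHANES background; and PBPK models. Section 3.10 states: "Primary analyses will focus on estimated cumulative PFAS serum levels".

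**Who gets which form.** Under Section 3.6.5.1 the short form goes to children whose parent is also an adult participant and the long form to the others. Attachment 16, the adult questionnaire, is listed, but its text is not in the material supplied.

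**The concern.** Section 3.9 needs the concentration in the water the child actually drank. Where a filter sits between the supply and the glass, nothing on either child form links the two. A child on filtered tap water still reports full tap cups, and those cups are multiplied by a concentration reconstructed for the well or system. The water-borne part of the estimate is then too high for that child.

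This matters because the estimate is the primary exposure. If some children in the top category were in truth less exposed, the real difference between top and bottom is smaller than the modelled one, and the exposure-response relation is flattened. Section 5 itself makes the study's usefulness depend largely on estimating historical serum levels with reasonable accuracy.

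**Working it through.** **1. Text check.** Long form B1 to B11 and short form B1 to B4 were read item by item. They contain source type, cups, addresses, move-in dates and the two maternal items. There is no filter or treatment item, and the documents supplied do not mention home filtration elsewhere. Section 3.6.5.1 names formula, juices and bottled water as habits to be covered, but not filters.

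**2. Can another input fill the gap?**
- Water data: the sampling results that Section 3.9 tells recipients to request come from intakes, supply and monitoring wells, the distribution system, purchased water and private wells. All lie upstream of a home device.
- Reported cups: a child who switches to bottled water reports fewer tap cups. A child who drinks filtered tap water does not.
- Measured serum: this does carry information on the dose absorbed. One blood draw cannot date a filter or separate filtering from lower intake, so any correction is partial and of unknown extent.

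**3. Overstatement for one child (assumed inputs).** Let t be the share of intake that was filtered and r the fraction removed. Modelled over true water-borne dose is 1/(1 − t·r):
- t = 0.25, r = 0.5: 1/0.875 = 1.14
- t = 0.5, r = 0.5: 1/0.75 = 1.33
- t = 0.5, r = 0.9: 1/0.55 = 1.82
- t = 1, r = 0.9: 1/0.10 = 10

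**4. Contrast and power (illustration).** The plan's own figures come first. Table 1 gives SD 29.3 mg/dL for child total cholesterol. With n = 2·SD²·(1.96 + 0.84)²/Δ², Δ = 4.6 gives 637 per stratum and Δ = 9.3 gives 156. Both match Table 1.

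2,000 children in quartiles are 500 per stratum, and 29.3·√(2/500) = 1.853. Power is Φ(Δ/1.853 − 1.96): 0.699 for 4.6 and 0.999 for 9.3.

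Now assume that a share s of the top quartile filtered throughout, that the reference quartile is unaffected, that the effect is linear in dose, and that the Table 1 difference belongs to the full modelled contrast. The contrast kept is 1 − s·r.

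| s | r | contrast kept | power, +4.6 | power, +9.3 |
|---|---|---|---|---|
| 0.1 | 0.5 | 0.95 | 0.655 | 0.998 |
| 0.3 | 0.5 | 0.85 | 0.560 | 0.989 |
| 0.5 | 0.9 | 0.55 | 0.276 | 0.788 |

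**5. Does the point need filter use to follow contamination?** A simulation of 400,000 children used ln concentration SD 1.2, ln intake SD 0.6 and a fixed background of 0.1 to 1.0 times the median water dose. Removal was 50% or 90%, over half or all of the period. The ratio of true to modelled top-versus-bottom-quartile difference in log serum was:
- filter use flat at 10%: 0.93 to just under 1
- use rising from 10% to 30% with concentration: 0.79 to 0.98
- use rising from 10% to 60%: 0.59 to 0.96

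For a comparison planned at 80% power, Φ(2.80·ratio − 1.96) gives about 78% at 0.98, 60% at 0.79 and 38% at 0.59. Even flat use lowers the contrast slightly, because background cushions the bottom quartile more than the top.

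Every filter figure in steps 3 to 5 is an assumption, and none of these calculations includes the measured-serum input.

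**The case against.** **Measured serum is a model input.** A reader might infer that children on filtered water are modelled at the full source concentration. Section 3.9 does not support that: serum measured in the study enters the estimate, and earlier results, where available, are used for validation. Only the water-borne part is exposed to the error. The supplemental analyses of measured serum in Section 3.10 do not depend on filter reporting. This objection stands and limits the claim.

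**Link to contamination.** A reader might infer that the error falls mostly on the most contaminated homes, since Section 3.5 says "wells with higher concentrations will be oversampled". That sentence governs whom to recruit and says nothing about filters. More filtering where households knew of the contamination is plausible, but it is an assumption.

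**Late knowledge.** Owners who filter because they know of contamination may have started late. With filtering over half the period and background at 0.2 to 0.5 times the median water dose, the simulated ratio is 0.94 to 0.98 for 10% to 30% use and 0.89 to 0.96 for 10% to 60% use, even where removal reaches 90%. The low ends in step 5 need 90% removal throughout, which is possible for young children but not shown to be typical.

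**Adult questionnaire.** Attachment 16 may hold a filter item that covers homes shared with the parent. This cannot be checked, so the short-form gap is conditional.

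**Recontact.** A reader might infer that the information is lost after the visit. The documents provide otherwise: the Attachment 10 script foresees contacting families again with clarifying questions, and Section 3.8.2 keeps contact details for that purpose. Later collection is possible, but costs more and relies on later recall.

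**Conclusion.** The point holds in limited form. Neither child form records home filtration or its start date, so the water-borne part of the primary exposure may be overstated for children who drank filtered tap water. The direction follows from the text; the size does not. The gap is firm for long-form children. For short-form children it holds unless Attachment 16 has such an item for the shared addresses.

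Under the assumptions shown, and with no correction by measured serum, the effect runs from negligible to material. In step 4, power for the +4.6 mg/dL cholesterol difference falls from 0.699 to between 0.655 and 0.276, while for +9.3 mg/dL it stays at 0.788 or above. These figures illustrate the range and do not estimate a loss. A reader might take them as an established power loss, but the documents give no filter use, no removal fraction and no link between filtering and contamination. What favours acting is that the forms as written leave the study unable to tell which end of the range applies, and the remedy is cheap.

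**What to change.** - **Long form (Attachment 15):** for the current home, the previous home and the B9 table, add *Was the drinking water at this address filtered or treated at home? Type* and *From (mm/yy)*.
- **Short form (Attachment 15a):** add the same two columns to B2, unless Attachment 16 already covers the shared addresses.
- **Maternal exposure:** add a matching item to the pregnancy and breastfeeding water questions (15, B10 and B11; 15a, B3 and B4).
- **Model:** enter the answers in the Section 3.9 model as a removal factor applied from the reported date, with a stated sensitivity range for the removal fraction.

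**Cost.** About a minute more per interview. Start dates will be recalled imperfectly, and the removal fraction has to be assumed and varied. The forms still carry placeholder OMB numbers, and Attachment 5c lists IRB and OMB approvals as pending, so the items can go in before approval.
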